2. SUMMARY OF PROPOSALS

2.1 ABSTRACT:

The detection of malarial retinopathy (MR) in cerebral malaria (CM) patients currently requires expensive equipment and extensive training. We have developed a computerized software-based analysis of retinal images obtained by handheld fundus cameras that is >90% specific. The purpose of this study is to evaluate the performance of a software in detecting malarial retinopathy in retinal images obtained using hand-held fundus cameras by non-ophthalmologist clinicians. The overall aim of the proposed study is to collect digital retinal image data of clinically diagnosed CM patients and utilize the images to develop and test the performance of software algorithms (ASPIRE) for detecting specific signs of MR and for detecting the presence of MR. The performance of the software will be measured against the binocular indirect ophthalmoscopy (BIO) examination (if available) performed by an ophthalmologist for determining the presence of MR (reference standard) and/or against the grading of established retinal graders. Participants between the age of 6 months and 12 years who present with coma, a positive malaria test, and clinical diagnosis of CM, will be enrolled at the time of admission at the respective participating hospital(s). The imager will be masked to MR detection results. The retinal images will be graded by an ophthalmologist for the detection of specific signs of MR. The retinal images will be used to develop and test algorithms for detecting specific MR lesions and overall MR presence. The sensitivity and specificity of the software algorithms against grader's image grading will be determined to evaluate the performance of each algorithm and its usability in identifying MR. This study would be a first step in the validation of retinal image analysis software for assessment of MR. The results of the

study will be used to inform initiatives to spread the use of software-based detection of MR to preclinical settings in which CM patients are seen. Results will also be useful in planning the studies to quantify the detection of MR lesions and analyze large datasets in objective manner.

LAY SUMMARY OF RESEARCH PROTOCOL

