To establish that our software-based test is non-inferior to the standard test (ophthalmologist’s reading of images), with sensitivity of 0.89 and specificity of 0.87; we will require a minimum number of disease-positive (MR-positive) “cases” of 366, and minimum number of disease-negative (MR-negative) “controls” of 234. In total, we will require a minimum sample size of 600 CM-diagnosed patients to validate our proposed test.

Once we enroll the minimum number of MR-positive and MR-negative patients required, we propose to validate the software-based test performance on the collected sample and verify if the resulting sensitivity/specificity is within the margin of difference. Upon verification, it can be concluded that the experimental test is non-inferior to the standard test within a non-inferiority margin of 7%.

Sampling procedure [11]

The procedure will be as follows:

1. Pupillary light response is checked and then pupils are dilated with 0.5% tropicamide and 10% phenylephrine, repeated after 10 minutes.
2. Ophthalmologist, clinician or nurse takes iNview photos (at least 8 photos: 4 optic disc center, 4 macula center)
3. Ophthalmologist, clinician or nurse takes VistaView photos (at least 8 photos: 4 optic disc center, 4 macula center)
4. Ophthalmologist, clinician or nurse takes Pictor-Plus photos (at least 8 photos: 4 optic disc center, 4 macula center)
5. The retinal photos captured by Pictor-Plus, VistaView, and iNview cameras may be transmitted to a laptop computer or smartphone automatically and analyzed instantaneously for image quality by a computer-based software. The software will either accept or reject each photo based on high or low image quality, respectively. A graphical display on a laptop computer or smartphone

will be shown to the imager (ophthalmologist, clinician, or nurse) that demonstrates the captured image and whether it was accepted or rejected.

6. The retinal photos captured by Pictor-Plus, VistaView, and iNview cameras will be analyzed instantaneously for detection of malarial retinopathy (MR) by a computer-based software. The imager (ophthalmologist, clinician, or nurse) will be masked to MR detection results due to non-interventional nature of this study.
7. The analysis of retinal photos for image quality and MR detection will be fully automatic and handled by a laptop computer or smartphone and will not require manual inputs or interference from the imager.
8. Ophthalmologist performs BIO when possible.

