To answer *study question #2*, sensitivity and specificity with 95% CI will be calculated for each of the following:

- presence or absence of MR (any hemorrhage, whitening or abnormal vessels) between:

To answer *study question #3*, positive predictive value (PPV) and negative predictive value (NPV) will be calculated to evaluate software algorithm’s performance in classifying a retinal image for presence or absence of each of the following MR lesions, against retinal grader’s grading for the presence of respective lesions.

The analyses described above will be performed for subgroups determined by malaria test results as well. It is not possible to mask the malaria status from the examining clinicians. The analysis results will be presented in form of tables.

DISSEMINATION OF THE RESULTS

Results of the study will be provided to VisionQuest Biomedical and NHERC in the final report, presented locally in Nigeria, and submitted to an international journal for publication. Standard rules for authorship on a final publication will apply.

A copy of the final report and any published paper(s) or abstracts of papers read at conferences out of the research findings will be submitted to each of the following:

1. VisionQuest Biomedical Inc.
2. University College Hospital, Ibadan, Nigeria
3. Amino Kano University, Kano
4. General Sani Abacha Specialist Hospital Damaturu
5. State Specialist Hospital Sokoto -
6. Massey's Children Hospital, Lagos Island

A copy of the data (including photos) will be distributed to all of the above institutions, if necessary, for use in future analysis upon agreement of the main investigators.

ETHICAL CONSIDERATIONS

Study personnel trained in human ethics will obtain informed consent from parents of study participants. The Principal and co-investigators will conduct on-site training sessions for Nigerian study staff who will be collecting study information and obtaining

consent from study participants. The study will be explained in detail to the local study staff. The basic principles of informed consent process, documentation of informed consent, protection of subjects' rights, confidentiality, and handling of data will be covered in these training sessions. All training sessions will be documented, and study staff monitored by the on-site project manager on a regular basis to ensure compliance with the principles of informed consent.

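### Lesion detection is assessed per image by PPV and NPV, which disagrees with the abstract and the objectives on metric and unit, and nothing is said about correlated photos of the same child

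*Combined protocol and SAP*

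**What the plan says.** Three places in the combined protocol and SAP bear on how lesion detection is judged.

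- **Section 2.1, Abstract.** "The retinal images will be used to develop and test algorithms for detecting specific MR lesions and overall MR presence". Sensitivity and specificity against the grader's image "grading will be determined to evaluate the performance of each algorithm and its usability in identifying MR".
- **Section 3.5, Specific Objectives.** The primary objective uses sensitivity and specificity, and the secondary objective uses PPV and NPV. Both concern classifying the patient as MR positive or MR negative.
- **Data Analysis.** For study question #2, "sensitivity and specificity with 95% CI will be calculated for each of the following"; the one item that survives is "presence or absence of MR (any hemorrhage, whitening or abnormal vessels) between", where the text breaks off. For study question #3, "positive predictive value (PPV) and negative predictive value (NPV) will be calculated to evaluate software" algorithm "performance in classifying a retinal image for presence or absence of each of the following MR lesions", against the grader. No confidence interval is mentioned for question #3, and the list of lesions does not appear in the text available.

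On the number of images, steps 2 to 4 of the Sampling procedure ask for "at least 8 photos: 4 optic disc center, 4 macula center" with each of three cameras. They do not say whether this is per child or per eye. Condition (c) lets camera steps be omitted, and step 5 has software accept or reject each photo. No section says how photos, eyes and cameras of one child are combined, or how their correlation enters a variance.

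**The concern.** The general objective (section 3.4) includes testing how well the software detects specific signs of MR. An analyst who follows the visible Data Analysis text would produce, for each lesion, a PPV and an NPV over images. Two things then go wrong.

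First, both quantities depend on the share of analysed images that show the lesion. That share reflects which children were enrolled, which fields were photographed and which frames passed the quality filter, as well as the algorithm. A lesion algorithm could not be compared fairly across cameras, sites or later studies from these figures alone.

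Second, several views of the same two eyes are not independent. An interval computed on the image count would overstate the information.

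There is also a gap in the other direction. Section 3.5 promises patient-level PPV and NPV for MR, but the only PPV and NPV line in Data Analysis is per image and per lesion. As written, that secondary objective has no matching analysis.

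**Working it through.** **The plan's own figure.** The plan gives no number for the image-level analysis. Its sample size is per patient. The printed formula is N_cases = (z_α + z_β)²/d² × [π_E(1−π_E) + π_S(1−π_S)/λ], with λ = 0.39/0.61, d = 0.07, one-sided 5% and 80% power.

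- Sensitivity 0.89: 317 cases and 203 controls (plan: 318 and 203).
- Specificity 0.87: 366 cases and 234 controls, total 600 (plan: the same).

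The figure reproduces, and nothing below changes it.

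**Step 1: dependence on lesion frequency.** Sensitivity 0.89 and specificity 0.87 come from Sample size determination. They are planning values for overall MR reading, borrowed here only for illustration. The per-image lesion frequency p is not in the documents, so it is assumed.

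PPV = 0.89p / [0.89p + 0.13(1−p)]; NPV = 0.87(1−p) / [0.87(1−p) + 0.11p].

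| p (assumed) | PPV | NPV |
|---|---|---|
| 5% | 0.27 | 0.99 |
| 10% | 0.089/0.206 = 0.43 | 0.99 |
| 30% | 0.267/0.358 = 0.75 | 0.95 |
| 40% | 0.356/0.434 = 0.82 | 0.92 |
| 80% | 0.97 | 0.66 |

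The algorithm is identical in every row.

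**Step 2: clustering.** The number of images per child, m, is 8 for one camera and 24 for three cameras (3 × 8), taking 8 as a per-child count. The within-child correlation ρ is not in the documents; 0.1 to 0.5 is assumed. The design effect is 1 + (m−1)ρ, and its square root is the factor by which a naive interval is too narrow.

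| m | ρ | Design effect | Factor |
|---|---|---|---|
| 8 | 0.1 | 1.7 | 1.30 |
| 8 | 0.5 | 4.5 | 2.12 |
| 24 | 0.1 | 3.3 | 1.82 |
| 24 | 0.5 | 12.5 | 3.54 |

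These are upper bounds for the stated m and ρ. PPV uses only software-positive images and NPV only software-negative ones, so the cluster size that counts is at most m. If 8 is meant per eye, m doubles to 16 or 48, and the factors become 1.58 to 2.92 and 2.39 to 4.95.

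**Step 3: a check on PPV itself.** A simulation used 600 children, mean lesion frequency 30%, and lesion frequency, sensitivity and false-positive rate each varying between children with correlation 0.1 to 0.5. The true PPV is 0.746.

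- 8 images per child: the naive standard error averages 0.0105, while the actual one is 0.0131 to 0.0211 (ratio 1.25 to 2.01). Coverage of a nominal 95% interval is about 88% to 67%.
- 24 images per child: 0.0061 against 0.0106 to 0.0209 (ratio 1.74 to 3.43). Coverage is about 74% to 44%.

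The ratios fall just under the bounds in step 2, as they should.

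**The case against.** A reader might infer four stronger things, and the documents do not support them.

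- **That lesions are assessed by PPV and NPV alone.** The list under question #2 breaks off and the lesion list under question #3 is absent, probably lost when the PDF was read. A per-lesion sensitivity item cannot be excluded, and section 2.1 promises one. What can be said is that the visible Data Analysis text does not carry that promise through.
- **That all photos are pooled and the result is reported too precisely.** No section says that frames, eyes and cameras go into one table, and no interval is stated for lesion PPV and NPV. The factors above apply only if images are treated as independent. The figure of 24 applies only to a child photographed with all three cameras.
- **That PPV and NPV say nothing about the algorithm.** They do describe it, at the lesion mix of this sample; they do not carry over to another mix.
- **That taking more frames by itself changes PPV.** Doubling every child's frames over the same fields leaves the lesion frequency unchanged. Only a different mix of fields or children moves it. The 4-plus-4 minimum and condition (c), which asks for consistency between patients, limit this somewhat.

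It is also fair that per-lesion detection is in the general objective but is not a numbered objective in section 3.5. Weighting each child equally is one choice of estimand among several.

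What survives is the disagreement between the three places on metric and unit, the dependence on lesion mix, and the absence of any rule for clustered images.

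**Conclusion.** The concern holds in a limited form. The abstract, the objectives and the visible Data Analysis text name different metrics and units for the same evaluation. Per-image PPV and NPV without sensitivity and specificity leave lesion performance tied to this sample's lesion mix: PPV runs from 0.43 to 0.82 for one fixed algorithm as the assumed lesion frequency goes from 10% to 40%. Clustering within the child is not addressed. If it were ignored in an interval, that interval would be too narrow by up to about 1.3 to 2.1 times (8 photos) or 1.8 to 3.5 times (24 photos).

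The lesion frequencies and within-child correlations are assumptions. The 0.89 and 0.87 are borrowed from overall MR reading. The patient-level primary comparison and its 600 patients are not affected.

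**What to change.** In Data Analysis, study question #3:

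1. For each lesion, report sensitivity and specificity beside PPV and NPV, from the same two-by-two table against the grader, separately by camera.
2. Give 95% CIs from a cluster bootstrap that resamples children, or from a cluster-robust method with the child as cluster.
3. Add patient-level PPV and NPV for MR status, so that the secondary objective in section 3.5 has its analysis, and state the rule that turns a child's photos and eyes into one result.
4. Optionally, add an analysis giving each child equal weight within camera, as a sensitivity check on unequal photo counts.

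The cost is slightly more analysis code and wider intervals. No further data or patients are needed.

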7. LIST OF ABBREVIATIONS

CM - Cerebral Malaria

MR - Malaria Retinopathy

BIO - Binocular indirect ophthalmoscopy

AI - Artificial Intelligence

GDP – Gross Domestic Product

10. APPENDIX

Appendix 1: Technical specifications of study devices:

Technical specifications for Pictor-Plus:

Volk's Pictor-Plus is a hand-held fundus camera with interchangeable modules. The four imaging modules include posterior and anterior segment, dermatoscopic, and otoscopic. The Pictor Plus provides 5-megapixel image (1536 X 1152 pixels) resolution and incorporates Wi-Fi technology for image transfer to a PC. An easy-access micro SD card slot may be used as a temporary storage unit for images. LED illumination is available in white or blue. The cobalt blue LED light allows for fluorescent imaging to detect dry eye, cuts, or rashes on the anterior segment of the eye. The white LED is used for fundus imaging. There are three focus modes: Auto, Auto Focus (AF) Assist, and Manual.

Specifications	Pictor-Plus
Resolution	5 Megapixels
Image dimensions	1536 X 1152
Image Format	JPEG and Video
Field of View	40 Degree
Pixel footprint	27 microns
Focus Range	-20 to +20D

Minimum Pupil Size	3 mm
Fundus Lighting	White LED
Weight	400g (~1 lb)
Power Supply	Rechargeable NI-MH Battery (3 hours)
Connectivity	Wi-Fi, USB

Technical specifications for iNview:

The Volk iNview is an ophthalmic camera used to acquire wide-angle digital color images of the retina (fundus) using an Apple iPhone or iPod. It is a combination product comprised of a mobile application (Apple App Store) and an indirect ophthalmoscopic lens attachment that fits for an Apple iPhone/iPod. The iNview device used in the proposed study is a simple adapter currently used on iPhone smartphone (<http://www.volck.com/index.php/volk-products/ophthalmic-cameras/volk-inview.html>).

This aligns the optics of the phone's camera with a light source. iNview camera obtains a wide 50-degree field of view to visualize the entire posterior pole in one image. Images taken with Volk iNview are stored with patient data and can be easily exported to a PC or Mac. iNview's user guide can be referred here: <http://www.volck.com/media/ifu/im088/im088english.pdf>

Technical specifications for VistaView:

The Volk VistaView is an ophthalmic camera used to acquire wide-angle digital color images of the retina (fundus) using a smartphone. The VistaView device used in the proposed study is a simple adapter used on smartphone (<https://www.volck.com/products/vistaview%E2%84%A2>). This aligns the optics of the phone's camera with a light source. VistaView is a mydriatic camera with following specifications:

